This study is randomized, double-blind, and sham-controlled. It is not triple-blind, i.e., the treating technician/coordinator will know the participant's study assignment. Participants, Investigators and assessors will be blind to treatment assignment. Specifically, no primary or secondary outcome data will be collected by, or seen by, the unblinded technician/coordinator. Additionally, exploratory outcomes will be self-administered with electronic data capture, and also will not be seen or collected by unblinded personnel. The technician/coordinator will have reduced contact with participants in comparison to Sponsor's previous eTMS clinical trials, due to increased remote data collection (also leading to reduced dwell time at the clinic), and barrier separation from technicians during as much of the EEG/ECG and treatment procedures as is physically possible.

Blinding challenges arise from visual, aural, and proprioceptive sources. Unless the connection of the coil assembly to the stimulator is hidden from the participant, the participant will know if the coil used is or is not properly engaged with the stimulator. The discharging coil head produces a clicking sound at the frequency of discharge that is audible to the participant. Additionally, the discharge of the coil head on the forehead is accompanied by a tapping sensation, sometimes strong enough to produce discomfort. The Test Phase of this trial relies on a combination of visual barriers and exclusion of persons who have in the past received any form of rTMS treatment to accomplish blinding of the participant.

Visual blinding is accomplished by concealing the stimulator end of the coil assembly. Two coils are attached to the stimulator, but only one of them is engaged properly with the stimulator so as to produce magnetic discharges at the coil head. The other is merely taped or tied in place for stability. The engaged coil is held to the forehead of active-assigned participants and the unengaged coil is held to the forehead of sham-assigned participants. The coil to be used with the participant is threaded through a barrier sufficient to hide whether the stimulator connection part of the assembly is engaged with the stimulator or merely tied down nearby.

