SAFETY

Adverse Events

An adverse event (AE) log will be kept. There will be data collection of AEs at all follow-up visits (F1, F2, F3) as well as recording of AEs reported to the treating personnel, or other medical personnel at the treatment site, at each treatment visit and AEs that are otherwise spontaneously reported. The Side Effects Questionnaire (SEQ) will be used to ensure full reporting of adverse effects of the study treatment and procedures. When an AE is noted by the Study Coordinator/Technician it will be escalated to the Site Investigator, or their medically qualified designee as appropriate, and in all cases for an SAE. All AEs and SAEs will be reported to the Data and Safety Monitoring Board. As noted above in the section on Unblinding, the PI will keep a log of unblinded adverse event data that may be used to call a for-cause DSMB meeting to conduct a safety review. AEs will be reported to the FDA and the IRB on the schedules determined by these oversight bodies, according to instructions for reporting differing types, severity, and relatedness, of AEs.

An adverse event (AE) is defined as any untoward medical occurrence in a participant treated with an investigational product and does not necessarily have to have a causal relationship with the treatment under investigation. An AE can therefore be any unfavorable and unintended sign, symptom, or disease temporally associated with the use of an investigational product, whether or not considered related to the investigational product.

Anticipated adverse device effects for purposes of both Stage 1 and Stage 2, in order of most common to least likely to occur, include:

- Headache and neck pain
 - \circ Sponsor's clinical use history ~15%.
 - rTMS: Headache ~23%, Neck pain ~12% of rTMS cases in general. (Machii, Cohen, Ramos-Estebanez, & Pascual-Leone, 2006)
 - Generally related to muscle tension.
 - Responds well to analgesics
 - Generally, resolves within the first week of therapy.
 - Short-term only. No long-term implications.
- Application site pain/discomfort
 - Sponsor's clinical use history ~5%
 - Generally, results from pressure placed against the scalp as opposed to stimulation.
 - Generally, resolves within the first week of therapy.
 - Short term only. No long-term implications.
- Eye pain
 - \circ Sponsor's clinical use history ~5%
 - Pressure may be felt in the back of the eyes during therapy, but this does not last more than a few seconds following the pulse train.

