An unanticipated adverse device event (UADE) is defined, in 21 CFR 812.3(s) as any serious ("serious" as defined above and in 21 CFR 312.32(a)) adverse effect on health or safety, or any life-threatening problem or death caused by, or associated with, a device, if that effect, problem, or death was not previously identified in nature, severity, or degree of incidence in the protocol and/or Instructions For Use (IFU), or any other unanticipated serious problem associated with a device that relates to the rights, safety, or welfare of the participant.

All adverse events that do not meet any of the criteria for SAEs or UADEs should be regarded as non-serious adverse events.

Progression of disease reflects lack of therapeutic efficacy and should not be treated as serious adverse events. However, other events or complications meeting the criteria for serious adverse events should be considered as a serious adverse event and should be reported to the IRB regardless of presumed relationship to the investigational treatment.

Adverse Event Assessment

All adverse events (AE), including the following, will be assessed by the Investigator or his or her medically qualified designee, and recorded on the study Adverse Event form according to the protocol and the Manual of Procedures:

- Observed or volunteered problems
- Complaints
- Physical signs and symptoms
- Medical condition which occurs during the study, having been absent at screening
- Medical condition present at screening which appears to worsen during the study

The need to capture AEs is not dependent upon whether or not the clinical event is associated with the use of the study treatment.

Severity will be assessed using the following definitions:

- Mild: Aware of sign or symptom, but easily tolerated
- Moderate: Discomfort sufficient to cause interference with usual activity
- Severe: Incapacitating, with inability to work or do usual activity

The relationship to Investigational Treatment will be assessed by the Investigator using the following criteria:

- Not Evidence exists that the adverse event definitely has a cause other than the study treatment (e.g., pre-existing condition or underlying disease, intercurrent illness, or concomitant medication) and does not meet any other criteria listed.

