Error checking will be implemented in the EDC, including real-time range checking at entry, specification of required fields, skip pattern specification, and within-form internal consistency checks. Data will be checked for omissions in as real-time as possible, with explanation for missing data. Periodic cross-form consistency checks, and batch error-checking will be followed by data quality queries. Errors will be corrected in a manner that leaves a complete audit trail. The audit trail for any change will include information showing the original value, the new value, the date and time the change was made, who made the change, and a brief reason why the change was made.

When participants enter data, clinic personnel will check the entries for errors and omissions. Periodic checks and inspections will be conducted for data completeness and logical inconsistencies. Any discrepancies or needed clarifications will be resolved via Data Quality Query (DQQ), wherein study data collection personnel will be asked to resolve issues. Site monitoring, also, will include resolution of any issues not resolved by the periodic DQQs.

At the conclusion of each stage of the trial, a final round of quality checking will occur, and all issues that can be resolved, will be resolved. After the last participant visit is entered, data will be reviewed by a Study Monitor/Biostatistician, and a final batch EDC system edit run will be done to ensure all queries and discrepancies have been addressed. Issues that cannot be resolved will be described in a memo to file and attached to any analyses. The DC will notify the Study Chair, Principal Investigator and IDE Sponsor that it considers the database ready for lock. An approval signature by the Study Chair, Principal Investigator and Sponsor will be acquired prior to study database lock. The DC will perform final database lock procedures per SOP. Thereafter, the database will be locked for that stage. All final statistical analyses will be conducted on datasets extracted from the locked database.

Data Security

When paper forms are used as the primary data collection medium, these source documents will be housed at the clinical site under lock and key.

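### In Stage 2 an unblinded technician/coordinator is a first point of capture for adverse events, and the escalation wording can leave it to that person which non-serious events reach the blinded Investigator

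*Combined protocol and SAP*

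**What the plan says.** **Who is blind.** The Blinding section states that "the treating technician/coordinator will know the participant's study assignment", whereas "Participants, Investigators and assessors will be blind to treatment assignment".

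**What is kept from unblinded staff.** The same section says that "no primary or secondary outcome data will be collected by, or seen by, the unblinded technician/coordinator", and that "exploratory outcomes will be self-administered with electronic data capture, and also will not be seen or collected by unblinded personnel". Adverse events are not mentioned in either sentence.

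**How events are captured.** The Adverse Events section provides for an event log, collection at F1, F2 and F3, spontaneous reports, and recording of "AEs reported to the treating personnel, or other medical personnel at the treatment site, at each treatment visit". The SEQ prompts for expected reactions and is scheduled at every treatment and follow-up visit (Table 5). Its description under Data to be collected has the participant indicate each symptom and its grade. It does not say who administers the form or who sees the answers.

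**How events move on.** The Adverse Events section says: "When an AE is noted by the Study Coordinator/Technician it will be escalated to the Site Investigator, or their medically qualified designee as appropriate". The sentence ends by requiring escalation of every SAE. The Adverse Event Assessment section says: "All adverse events (AE), including the following, will be assessed by the Investigator or his or her medically qualified designee".

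**Checks on participant entries.** The Data Integrity section says: "When participants enter data, clinic personnel will check the entries for errors and omissions". It does not give the blinding status of those personnel.

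**The concern.** Stage 2 safety is characterised by the incidence, severity, relatedness and type of adverse events, listed by arm for the DSMB. Such a comparison is fair only if an event has the same chance of being recorded and graded in both arms. Here a person who knows the arm is one of the first to hear of it, and may have discretion over whether a non-serious event goes further. Someone who expects effects from active stimulation could pass on more of them in that arm. Someone who regards them as trivial and expected could pass on fewer. The bias could run either way, and the blinded Investigator cannot grade an event that never arrives. The plan already guards its efficacy and exploratory outcomes against this problem but does not extend the guard to its safety outcome.

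**Working it through.** No figure in the plan bears on this point, so the check sets the sections side by side.

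1. **Contact and knowledge.** The Blinding section makes the technician/coordinator unblinded. The Adverse Events section makes treating personnel one of the recipients of reports at treatment visits. An unblinded role is therefore a first point of capture, though not the only one.

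2. **Reach of the protection.** Primary, secondary and exploratory outcomes are named as shielded. Adverse events, listed separately as the Safety Outcome in the synopsis, are not.

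3. **The escalation sentence.** It can be read in two ways.
   - *As appropriate* qualifies only the choice between Investigator and designee. Every event would then be escalated already, and the closing words on SAEs would add nothing.
   - *As appropriate* qualifies the escalation itself. The closing words then do real work: SAEs always, other events by judgement.

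   The second reading gives every part of the sentence a purpose and is the more natural one. It conflicts with the Adverse Event Assessment section, which has all events assessed by the Investigator or designee. Even on the first reading the sentence is ambiguous beside that section.

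4. **Can later visits make up the loss?** The Adverse Events section lists 12 anticipated effects with the time each is expected to last:

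| Stated course | Effects | Count |
|---|---|---|
| Gone in the first 1–3 days | eye pain, dizziness, dental/jaw pain | 3 |
| Gone within the first week | headache/neck pain, site pain, mania/hypomania, insomnia, auditory effects, muscle twitching | 6 |
| Gone within the second week | anxiety/depression, cognitive changes | 2 |
| Single, very short episode | seizure | 1 |

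   So 3 + 6 = 9 of 12 are expected to be over by day 7. Table 5 opens the F1 window at RD+10, which is 10 − 7 = 3 days later at the earliest, and closes it at RD+21. The SEQ asks whether the participant is experiencing a symptom, that is, about the present. No recall period for adverse events at F1 is given. For most anticipated effects, capture may therefore rest on the treatment visits, where the unblinded role works.

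5. **Participant-entered outcome data.** The Data Integrity section assigns the check to clinic personnel in general. The Blinding section specifically bars the unblinded technician/coordinator from seeing primary or secondary outcome data. The specific rule governs the general one, so the gap is a missing cross-reference.

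6. **Size.** A bias figure would need the share of events passed on in each arm. The documents give no such share, so none is computed.

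**The case against.** The strongest reply is that escalation is not recording. The protocol promises a log, recording of events reported at treatment visits, reporting of all AEs and SAEs to the DSMB, and evaluation of all events from onset. It names other routes: other medical staff, spontaneous reports, three follow-up visits, and a questionnaire answered by the participant. An event not escalated at once is not thereby shown to be lost. The technicians are also acknowledged to be unavoidably unblinded.

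Much of this stands. Loss of events is possible, not demonstrated, and the technician is one route among several. The reply does not remove the conflict over which events the Investigator assesses, and it leaves open who administers the SEQ. Severity and relatedness are graded by the Investigator or designee, so an event that is logged but not passed on would not receive the blinded assessment the plan promises.

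A reader might infer three stronger things, none of which the documents support:

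- *That the technician alone knows the allocation.* Under Unblinding, the PI keeps the assignment file. Under Analysis of Safety, the DSMB, Study Chair and PI are unblinded for AE data. The PI and Study Chair are stated not to collect data or treat participants at the sites. What is accurate is that the technician/coordinator is the unblinded role in direct contact with participants.
- *That PCL-5 scores can be shaped by allocation through the entry checks.* The Blinding section bars the unblinded role from those data, the PCL-5 is self-report, and corrections leave an audit trail.
- *That the bias amounts to some number of percentage points.* The documents' headache figures run from about 15% (sponsor's clinical use, with neck pain) and about 23% (rTMS in general) to 55.1–58.2% (a review of rTMS studies), but no capture rate accompanies any of them. Analysis of Safety plans listings and summaries, with no between-arm test against which to set such a number.

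**Conclusion.** The point holds as a weakness in how the Stage 2 safety outcome is ascertained. An unblinded role in contact with participants is a first point of capture. The escalation wording most naturally gives that role discretion over non-serious events, contrary to the Adverse Event Assessment section. The protection from unblinded staff does not cover adverse events. Differential ascertainment by arm is therefore possible, in either direction and of unknown size.

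This rests on two assumptions: that *as appropriate* qualifies the escalation, and that short-lived events not passed on during treatment are not reliably recovered at F1. If the first fails, the two sections still need to be reconciled and SEQ administration still needs to be stated. The primary efficacy analysis is not called into question; for outcome data the plan needs only a clarifying cross-reference. The change is worth making because it is cheap and uses arrangements already in the plan.

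**What to change.** 1. **Adverse Events section.** Reword so that every event noted by the technician/coordinator is recorded and passed to the blinded Investigator or a blinded, medically qualified designee. This brings it into line with the Adverse Event Assessment section.
2. **SEQ.** Have participants enter it directly in the EDC at each visit, with the entries routed to the Investigator. This extends to adverse events the self-administered electronic approach that the Blinding section already uses for exploratory outcomes. Say so in that section.
3. **Data Integrity section.** Add that the clinic personnel who check participant entries exclude the unblinded technician/coordinator, as the Blinding section already requires for outcome data.

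The technician keeps all immediate safety duties.

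Cost: EDC form routing and about three sentences of protocol text. In use, it adds a few minutes per visit and more minor events for the Investigator to grade. There is also some chance that entries describing sensation at the coil hint at the arm, since tapping is absent under sham.

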	3. Provisional diagnosis of PTSD according to Veterans
	Administration PCL-5 rubric fulfillment AND cutpoint score of 31 or above
	 Positive identification as either a Veteran, or First Responder
	(e.g., emergency medical service provider, firefighter, or any
	other emergency response personnel)
	Exclusion Criteria
	Participants will be excluded from study participation if one or more of the following exclusion criteria apply:
	 Uncontrolled medical, psychological or neurological conditions including, but not limited to:
	a. Uncontrolled psychosis or mania
	b. Uncontrolled seizure disorder or EEG
	abnormalities that indicate risk of seizure, i.e.,
	epileptiform discharges during the EEG recording
	c. Uncontrolled cardiac, pulmonary, or endocrine disorder (e.g., diabetes)
	d. Acute pain or illness
	e. Active, untreated addiction to prescription drugs,
	alcohol or illicit substances* (not including THC/CBD, which is available in many states under
	medical prescription or for recreational use)
	f. Clinically significant medical condition or
	abnormality that in the Investigator's judgment
	might pose a potential safety risk to the subject or
	limit the interpretation of the trial results
	2. Pregnant, or female unwilling to use effective birth control during
	the course of the trial (unless cleared for participation by an obstatizion/gunacelogist)
	obstetrician/gynecologist)3. Presence of aneurysm clips or coils, cochlear or ocular implant,
	cortical epidural stimulator, deep brain stimulator, pacemaker or
	defibrillator, retained intracranial metal foreign body (bullets,
	shrapnel – excluding titanium and oral implants), steel stents or
	shunts, active vagal nerve stimulator, ventriculoperitoneal (VP)
	shunt
	4. Past exposure to metal fragments, permanent piercings, and/or
	other possible metal sources in the head and neck
	5. Unwilling or unable to adhere to the study treatment, data
	collection schedule, or study procedures, or any condition, that in

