Participants will be excluded from study participation if one or more of the following exclusion criteria apply:

- 1. Uncontrolled medical, psychological or neurological conditions including, but not limited to:
 - a. Uncontrolled psychosis or mania
 - b. Uncontrolled seizure disorder or EEG abnormalities that indicate risk of seizure, i.e., epileptiform discharges during the EEG recording
 - c. Uncontrolled cardiac, pulmonary, or endocrine disorder (e.g., diabetes)
 - d. Acute pain or illness
 - e. Active, untreated addiction to prescription drugs, alcohol or illicit substances* (not including THC/CBD, which is available in many states under medical prescription or for recreational use)
 - f. Clinically significant medical condition or abnormality that in the Investigator's judgment might pose a potential safety risk to the subject or limit the interpretation of the trial results
- 2. Pregnant, or female unwilling to use effective birth control during the course of the trial (unless cleared for participation by an obstetrician/gynecologist)
- 3. Presence of aneurysm clips or coils, cochlear or ocular implant, cortical epidural stimulator, deep brain stimulator, pacemaker or defibrillator, retained intracranial metal

foreign body (bullets, shrapnel – excluding titanium and oral implants), steel stents or shunts, active vagal nerve stimulator, ventriculoperitoneal (VP) shunt

- 4. Past exposure to metal fragments, permanent piercings, and/or other possible metal sources in the head and neck
- 5. Unwilling or unable to adhere to the study treatment, data collection schedule, or study procedures, or any condition, that in the judgment of the Investigator might prevent the participant from completing the study
- 6. Inability to calculate the EEG intrinsic alpha frequency at Baseline
- 7. Current participation in any interventional research protocol
- 8. History of any type of ECT or rTMS
- 9. History of intracranial lesion or increased intracranial pressure
- 10. History of ischemic or hemorrhagic stroke
- 11. History of other neurologic conditions with associated cerebral damage
- 12. Family history of epilepsy or seizure in a first degree relative
- 13. An elevated risk of suicide or violence to others
- 14. A personal history of epilepsy or seizure

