Non-therapeutic effects of the stimulation equipment are mitigated with a combination of exclusion criteria, treatment room setup, and removing sensitive objects from proximity with the stimulator. The MagVita equipment magnetic field is the therapeutic element in eTMS treatment and is therefore required to be present. Its effects on other equipment, and especially participant implants must be mitigated or nullified. Treatment rooms will be set up to prevent the proximity of the MagVita device to sensitive equipment. Additionally, eligibility criteria for the trial exclude participants with implants that are sensitive to the strong magnetic field. These include: intracranial implants (e.g., aneurysm clips, shunts, stimulators, cochlear implants, stents, or electrodes) or any other metal object within or near the head, excluding the mouth, which cannot be safely removed, as well as implanted cardiac pacemakers, implantable cardioverter defibrillators (ICD), cervical or thoracic spinal cord stimulator, ventriculoperitoneal (VP) shunt, metal stents or shunts, medication dispensing devices, or any other active or non-active metal implants. There is a risk of permanent damage to any implanted battery-operated generator or lead/paddle. That damage could require revision surgery. Trial SOPs will include instructions regarding placement of wearable or removable devices or objects as well (for example, cell

phones, credit cards, ignition keys, jewelry, eyeglasses, and non-removable piercings). The informed consent process will stress the importance of giving a full and accurate history regarding the presence vulnerable or metal objects.

Emergency Action Plans

All sites will have specific emergency action plans to respond to seizure, cardiovascular events, elevation of risk of suicide or violent behavior, or a general injury. Plans and descriptions of resources will be included in the Manual of Procedures, which will include procedures for response and location of responding resources. Appropriate plans will be put into place for sites, as initiated to the study, depending on their intrinsic resources. All coordinators and technicians will be trained:

- to respond to seizure
- to react appropriately and anticipate violent behavior
- to recognize suicidal ideation
- to respond to general injury

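### The safety section says people with spinal cord stimulators or medication dispensing devices are excluded, but neither copy of the exclusion list names these devices.

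*Combined protocol and SAP*

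**What the plan says.** The Technical and Protocol Risk Mitigation section opens its paragraph on field effects this way: "Non-therapeutic effects of the stimulation equipment are mitigated with a combination of exclusion criteria, treatment room setup, and removing sensitive objects". It then makes a factual statement about the entry rules: "Additionally, eligibility criteria for the trial exclude participants with implants that are sensitive to the strong magnetic field". The implants it lists include "cervical or thoracic spinal cord stimulator, ventriculoperitoneal (VP) shunt, metal stents or shunts, medication dispensing devices", and the list closes with a catch-all for other metal implants, active or not. The reason given is serious: "There is a risk of permanent damage to any implanted battery-operated generator or lead/paddle. That damage could require revision surgery".

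The implant criterion itself is exclusion 3, which reads the same in the Study Synopsis and in the Participant Population section. The body copy begins "Presence of aneurysm clips or coils, cochlear or ocular implant, cortical epidural stimulator, deep brain stimulator, pacemaker or defibrillator", goes on to retained metal inside the skull, and ends with "steel stents or shunts, active vagal nerve stimulator, ventriculoperitoneal (VP) shunt". Exclusion 4 adds "Past exposure to metal fragments, permanent piercings, and/or other possible metal sources in the head and neck". Exclusions 1f and 15 allow the investigator to exclude anyone whose condition might be a safety risk. They name no device.

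**The concern.** The safety section tells its readers that a categorical exclusion exists. The exclusion list does not contain it for spinal cord stimulators or medication dispensing devices. Under Study Design, Stage 2, subjects who complete baseline and meet the inclusion and exclusion criteria are randomized, so the list is the operative rule.

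The gap is easy to miss. Exclusion 3 names three other implanted nerve or brain stimulators (cortical epidural, deep brain, active vagal nerve). Someone working from the list alone could take the absence of spinal cord stimulators as deliberate.

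At stake is damage to an implanted generator or lead in someone the protocol says is kept out. No endpoint, sample size or analysis is affected.

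**Working it through.** The plan gives no figure on this point, so there is none to reproduce. The check sets the safety section's list against exclusion 3 (both copies) and exclusion 4.

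| Implant the safety section says is excluded | Exclusion 3, both copies | Exclusion 4 (head and neck) | Result |
|---|---|---|---|
| Intracranial implants | Main types named | Covers other metal in the head | Covered |
| Pacemaker, implanted defibrillator | Named | Not needed | Covered |
| Ventriculoperitoneal shunt | Named | Not needed | Covered |
| Cervical spinal cord stimulator | Not named | Arguably reached through the neck | Arguable |
| Thoracic spinal cord stimulator | Not named | Out of reach | Gap |
| Medication dispensing device | Not named | Out of reach below the neck | Gap |
| Metal stents or shunts | Steel only | Covers head and neck | Partial |
| Any other active or non-active metal implant | No such clause | Covers head and neck only | Partial |

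**Count.** Two device types (spinal cord stimulator, medication dispensing device) against two copies of the list gives 2 × 2 = 4 checks, with 0 matches. The copies carry the same text, so in substance this is two missing items. For spinal cord stimulators the clear gap is the thoracic type.

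**Other criteria.** Exclusions 1f and 15 could be used to exclude such a person, but only by judgement.

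**Other safeguards in the text:**

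- The Consent Process stresses accurate reporting of metal and biomedical devices.
- A TMS Screening Form is completed at baseline (Tables 4 and 5), with a medical history and physical.
- Baseline Visit and Eligibility Determination has eligibility decided after baseline results are reviewed, and requires the site investigator to review a checklist and confirm in writing.

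The documents do not show the content of the screening form or the checklist. These steps could identify a device, but nothing in view makes a thoracic stimulator or a medication device disqualifying once it is reported.

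**Steel versus metal.** Shunts of the ventriculoperitoneal type are named and exclusion 4 covers the head and neck. The difference therefore matters only for non-steel stents or shunts below the neck, and it may be intended.

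**The case against.** The strongest reply is that this is incomplete cross-listing, not conflicting rules. The safety section is current protocol text and itself says these people are excluded; the list is merely shorter. An investigator who reads both has explicit guidance for applying exclusions 1f and 15 to a generator-based device. A TMS-specific form must be completed, and baseline results reviewed, before eligibility is set, and nobody can say that the form or the checklist omits these devices. It can also be said that a thoracic device lies far from a coil at Fz, and that the count of four treats one list as two.

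Part of this stands. The safeguards are real, they lower the chance of wrongful enrolment, and the count is better read as two items.

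The rest does not remove the discrepancy. The safety section does not present itself as adding exclusions; it reports what the eligibility criteria contain, and that report is wrong for these devices. The safeguards are either discretionary or of unseen content. Distance is not the rule behind exclusion 3, which already names pacemakers and defibrillators, and the sponsor's own text classes these implants as field-sensitive. Up to three sites may be added in Stage 2, which makes a uniform written rule more useful than reliance on judgement.

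**Conclusion.** The concern holds. The protocol claims an eligibility control that its exclusion list does not contain for two device types: spinal cord stimulators (clearly the thoracic type) and medication dispensing devices.

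What is established is the absence of a named criterion, not that anyone with such a device would be enrolled. The conclusion rests on exclusions 3 and 4 as printed, and on reading exclusion 4 as possibly covering a cervical stimulator. How many candidates might be affected cannot be estimated, because the documents give no implant prevalence.

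This should be fixed. The likelihood is unquantified and partly mitigated, but the stated harm could mean surgery and the correction is simple. The steel and metal wording is a lesser point.

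**What to change.** In exclusion 3, in both the Study Synopsis and the Participant Population section, add a spinal cord stimulator at cervical or thoracic level, an implanted medication dispensing device, and any other active implanted device. The last item matches the safety section's warning about any battery-operated generator. Put the same list in the eligibility checklist.

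Have the medically qualified investigators reconcile steel with metal stents and shunts, in whichever direction they judge right. Limit the safety section's closing catch-all to field-sensitive implants, which is what its opening statement already implies.

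The reverse correction, cutting the safety section back to match the list, would also make the text consistent. It would withdraw a protection the sponsor says it provides.

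The cost is wording in three places plus the checklist, with no added procedure and no statistical effect. Some candidates with active implants become ineligible by rule. Their number is unknown, but the safety section already says such people are excluded.
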